### **Significance**

Data compiled by CDC in 2011-2012 showed that there were 1,383,700 residents in NHs. Also about 4,742,500 patients received services from home health agencies, and 1,244,500

patients received services from hospices, collectively accounting for much of the frailest in the US. Overall, these provider sectors served over 8 million people annually (2013). Our study will focus on residents in long term care (LTC) facilities, but the findings of our study are highly relevant to persons frail enough to require such services in all of settings where the vast majority are at least 65 years old and thus appropriate for Fludax or HD, influenza vaccines licensed for this age group.

The SD influenza vaccine has diminished efficacy in the older population with the more debilitated LTC residents being among the worst responders yet with the highest mortality. Deaths due to pneumonia and influenza and chronic lung disease were 20 times higher among NH residents compared to community residents (Menec et al., 2002). **The current availability of two vaccines specifically for the elderly that both appear to work better than SD vaccine begs the question: is the newer and less-costly Fludax vaccine non-inferior or even superior to HD vaccine?** The proposed study aims to initially address non-inferiority as this is feasible in the clinical trial R01 grant structure and a critical first step to obtain head-to-head data from the same trial, cohort and vaccine years. Our proposed study itself may provide direct guidance on vaccine usage or inform a future trial assessing actual superiority should that be appropriate based on the results of our study.

HD vaccine is increasingly used by older Americans despite its greater cost over the SD vaccine and no preferential recommendation by the Advisory Committee on Immunization Practices (ACIP), the CDC committee responsible for making the vaccine recommendations for the U.S.. A finding of non-inferiority in the primary endpoint would provide a strong rationale to consider using Fludax over HD that could result in some cost avoidance across large long-term care system in the U.S. We are not powered for a superiority analysis but in a non-inferiority trial if the findings are substantial enough they may show superiority.

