##### **Secondary:**

Aim 2: Secondary objective: To determine if Flud has greater heterologous immunity than HD vaccine.

HAI, NAI, SVN assays will be performed with heterologous A/H3N2 strains to determine if Flud has an increased breadth of both B and T cell responses as would be predicted from an adjuvanted vaccine.

Aim 3: Pilot clinical objective: To determine if Flud has similar protective efficacy to HD vaccine. We will perform a record review and obtain blood 2-4 weeks after the influenza season is over. From a record review and speaking with the Director of Nursing, we will obtain dates and diagnoses of influenza, hospitalizations, any "influenza like illness" (ILI), and other illnesses, diagnostic tests, and hospitalizations during the study participation period. From the remote blood sample, we will determine if there is serologic evidence of influenza infection with a 4-fold titer rise beyond the post-vaccine titers. In exploratory analysis we will compare efficacy of prevention of influenza infection of Flud vs. HD using the record review and laboratory assessments. We will also be able to examine the concordance in this long term care population between record review and titer rise methods as evidence of infection that may aid in future study design.

Aim 4: Pilot objective: To compare the immunogenicity of recombinant flu vaccine (FLUBLOK) to the AD and HD influenza vaccines.

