After a resident is consented and found still eligible, they will be randomized using the UH based study database, RedCap, to receive one of the two licensed study influenza vaccines. Subjects will be assigned a donor code at that time that does not indicate which vaccine they have received so the lab analysis can remain blinded. Study staff will bring enough supply of each vaccine for either type of randomization and maintain the cold chain according to pharmacy policy so unused vaccine can be returned to the UH monitored study refrigerator. Vaccine will be given by research nurse or physician study staff or the clinical nurse at the long term care facility, since it is a standard of care vaccine that would have been given by that nurse even if they are not in the study. The first blood draw will be up to 2 weeks prior to the vaccine, or right before the vaccine is given. All blood draws will be obtained by the study research nurse.

Then at 4 weeks +/- 3 days we will return and draw the second blood draw. The third blood draw will be obtained 2-4 weeks after the influenza season is over, based on the CDC

surveillance in our region for that season when rates are near the offseason baseline. Typically that means the final blood draw will be sometime in April or early May of each season.

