### **Plan to monitor adverse events**

Subjects will have external monitoring while in the study as they are all long-term care residents. The LTC facilities are required to report any vaccine associated adverse events and we will have them cc us if any are reported. These vaccines are well tolerated and have very few severe adverse side effects reported. The sites will therefore notify us if there are any SAE in the 4 weeks between the first two blood draws. We will then report immediately any SAE to the IRBs. Virtually all SAE that would occur in this population would be vastly more likely due to issues related to their age and co-morbidities rather than vaccine related. Also there is already a mechanism in place for vaccine adverse event reporting (VAERS). Since both vaccines are part of FDA-approved and ACIP-recommended routine care, additional oversight and monitoring above standard mechanisms is not warranted. As the study is still formally a clinical trial we will still monitor the events reported through the established mechanism. Our LTC sites will be instructed to notify us with any events to subjects. We will also be on site at week 4, at the minimum, for the second blood draw and for an in person assessment as well. The LTC sites will be visited at the follow-up blood draw at 4 weeks unless some SAE evaluation would require a visit earlier. The vaccine is part of what would normally be routine care at the LTC sites, so they should not need extensive specific monitoring.

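### Aim 3 does not collect death, and its serologic endpoint exists only for residents alive and drawn after the season, so that comparison is conditional on survival

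*Combined protocol and SAP*

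**What the plan says.** Aim 3 is a pilot clinical objective: "To determine if Flud has similar protective efficacy to HD vaccine". It draws on two sources.

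- **Record review, with input from the Director of Nursing.** The list opens with "we will obtain dates and diagnoses of influenza, hospitalizations, any" influenza-like illness (ILI), and closes with "and other illnesses, diagnostic tests, and hospitalizations during the study participation period". Death does not appear.
- **Serology.** A case is "serologic evidence of influenza infection with a 4-fold titer rise beyond the post-vaccine titers". Under Study procedures, "The third blood draw will be obtained 2-4 weeks after the influenza season is over".

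The analysis is labelled exploratory: "In exploratory analysis we will compare efficacy of prevention of influenza infection of Flud vs. HD using the record review and laboratory assessments". The Data analysis plan gives no Aim 3 outcome definition, no denominator, and no rule for deaths or missing third draws.

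Deaths could reach the study through safety reporting. The Plan to monitor adverse events states: "The sites will therefore notify us if there are any SAE in the 4 weeks between the first two blood draws". The same section asks facilities to report events to subjects more generally, with no stated window, but nothing carries those reports into Aim 3.

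The Significance section stresses mortality in this population: "Deaths due to pneumonia and influenza and chronic lung disease were 20 times higher among NH residents compared to community residents".

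**The concern.** Survival to the third draw comes after randomisation and can be affected by the infection being counted. A resident who dies of influenza leaves both the numerator and the denominator of the serologic rate. If the vaccines differ in how often an infection is fatal, the serologic comparison is distorted in favour of the arm where more infections kill. A resident who dies in the facility of an untested respiratory illness, without hospital transfer, may leave no Aim 3 event beyond a possible ILI or illness note.

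Two things are at stake. The trial's only clinical comparison would not show deaths by arm, although mortality is a large part of its stated rationale. And the planned check of agreement between record review and titer rise, meant to inform later studies, would rest on survivors alone.

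**Working it through.** The plan gives no figure for this comparison, so there is nothing to reproduce. The calculation below shows direction and rough size.

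**Inputs from the documents.** 500 residents randomised 1:1, so 250 per arm (Study design); serologic case definition (Aim 3); timing of the third draw (Study procedures).

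**Assumed inputs.** The documents give no infection risk, case fatality or absolute death rate. Assumed: infection risk *p* of 10-12%; influenza case fatality *c* of 5-30%; share *s* of fatal influenza recorded before death, 0-100%.

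**1. Serologic risk among survivors.** Per person randomised, *p*(1−*c*) are infected and survive, and 1−*pc* do not die of influenza. Observed risk = *p*(1−*c*)/(1−*pc*). Deaths from other causes that are independent of infection and equal between arms multiply both terms by the same factor and cancel.

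For *p* = 0.10: *c* = 0.05 gives 0.095/0.995 = 9.55%; *c* = 0.20 gives 0.080/0.980 = 8.16%. The ratio is 0.855.

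| Infection A / B | Fatality A / B | Influenza deaths per 250, A / B | Serologic risk A / B | Ratio B/A | True infection ratio |
|---|---|---|---|---|---|
| 10% / 10% | 5% / 10% | 1.25 / 2.5 | 9.55% / 9.09% | 0.952 | 1.00 |
| 10% / 10% | 5% / 20% | 1.25 / 5 | 9.55% / 8.16% | 0.855 | 1.00 |
| 10% / 10% | 5% / 30% | 1.25 / 7.5 | 9.55% / 7.22% | 0.756 | 1.00 |
| 10% / 12% | 20% / 20% | 5 / 6 | 8.16% / 9.84% | 1.205 | 1.20 |
| 10% / 12% | 5% / 20% | 1.25 / 6 | 9.55% / 9.84% | 1.030 | 1.20 |
| 10% / 12% | 5% / 25% | 1.25 / 7.5 | 9.55% / 9.28% | 0.972 | 1.20 |

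The fourth row shows that equal fatality leaves the ratio essentially intact.

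**2. When the direction reverses.** With 10% versus 12% infection and 5% fatality in arm A, set B's observed risk equal to A's (*t* = 0.09548): *c* = (0.12 − *t*)/(0.12 × (1 − *t*)) = 0.02452/0.10854 = 0.226. Arm B looks better only if its case fatality exceeds about 23%, against 5% in arm A.

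**3. Effect of record review.** If a case counts when found by either source, over all randomised, the risk is *p*(1−*c*) + *pcs*. For 10% infection in both arms and 5% versus 20% fatality:

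- *s* = 0: 0.080/0.095 = 0.842
- *s* = 0.5: 0.090/0.0975 = 0.923
- *s* = 0.8: 0.096/0.099 = 0.970
- *s* = 1: 1.00

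**4. Size against chance.** The 0.855 corresponds to 20 cases in 245 against 23.75 in 248.75. The standard error of the log ratio is √(1/20 − 1/245 + 1/23.75 − 1/248.75) = 0.290, so the 95% interval is about 0.48 to 1.51.

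**5. Counting influenza death as an event.** Infection or influenza death over all randomised returns the true ratio, 1.00 or 1.20, if cause of death is recorded correctly.

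**6. All-cause death inside the composite.** With a true infection ratio of 1.20 (10% versus 12%) and independent other-cause death of 10%: (1 − 0.88×0.90)/(1 − 0.90×0.90) = 0.208/0.190 = 1.09. With 20%: 0.296/0.280 = 1.06.

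**The case against.** The strongest reply is that the bias needs case fatality per infection to differ between two active, enhanced vaccines, and nothing in the documents suggests a large difference. That stands. A reader might infer that a vaccine with more influenza deaths will generally look more protective. The documents do not support this: at equal fatality the ratio is 1.205 against a true 1.20, and even with a fourfold difference in fatality (5% versus 20%) the arm with more infections still looks slightly worse, at 1.03.

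Second, Aim 3 does not rest on serology alone. The record review spans the participation period and includes ILI and other illnesses. Recruitment procedures have facility staff go over enrolled residents' conditions at the end of participation. The consent section keeps residents who refuse a draw in data collection. Many fatal cases would therefore leave a record. This stands too: the distortion applies fully to the serologic half and, in the record half, only to fatal influenza that was never noted. It does not remove the gap, because nothing commits the study to recording deaths, reporting them by arm or using them in Aim 3.

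Third, the number of residents without a third draw might be taken as the size of the problem. It is not: deaths unrelated to influenza and balanced between arms do not cause this bias.

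Fourth, Aim 3 is exploratory and its estimates will be imprecise. That limits the weight of the point, but a few chart fields are still worth adding. The objection to an all-cause death composite is also sound: it pulls a true difference toward similarity in an aim that asks about similarity.

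**Conclusion.** The point holds as a cheap improvement to an exploratory aim. As written, the plan yields a survivor-only serologic comparison, loses fatal influenza that was neither diagnosed nor noted, and shows no deaths by arm.

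Under assumed rates (10% infection in both arms, 5% versus 20% fatality) the serologic ratio is 0.855 instead of 1.00. It moves to 0.952 if fatality is 5% versus 10%, and to no material bias if fatality is equal. Adding record review to serology brings the combined ratio to 0.923-0.970 when 50-80% of fatal influenza is recorded before death. All these rates are assumptions.

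The HAI co-primary endpoints use the 4-week sample and are not affected, so the finding should not be read as a threat to the non-inferiority conclusion.

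**What to change.** In Objectives, Secondary, Aim 3, with matching text in the Analysis Plan:

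1. Add date and recorded cause of death, and date of transfer out of the facility, through the end of the season, to the planned record review for every randomised subject, including those with no third draw.
2. Make the record-based comparison over all randomised subjects, with influenza-related death counted as an event alongside the outcomes already listed.
3. Show all-cause death separately by arm, outside the composite.
4. Label the serologic rate as a survivor-only result, and give the number dead or otherwise undrawn per arm.

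The cost is a few extra fields in a chart review that is already planned, plus protocol wording; no extra visit or blood is needed. The main downside is some misclassification of recorded cause of death, which the separate all-cause table helps a reader to judge.

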### **Study design including population to be studied, recruitment procedures and available resources**

We propose a non-inferiority randomized clinical trial to enroll 500 Long Term Care residents age 65 and older to receive either Fluvad or HD vaccine at 1:1 ratio. Blood will be sampled pre- and post-vaccine and post-influenza season and coded for blinded laboratory analysis. The FLUBLOK pilot objective will be a substudy of the current AD Fluvad vs. HD Fluzone study (UH IRB 10-27-29), and subjects will be consented on a separate FLUBLOK ICF.

**Population:** 500 subjects age 65 and older living in long-term care facilities in Northeast Ohio area. Up to an additional 120 subjects will be added to FLUBLOK substudy.  
50:50 male:female ratio.

**Study Duration:** 3 years

**Subject Duration:** estimated 6-8 months with patient contact

### **Recruitment procedures**

We will recruit from approximately 40 community long term care facilities in Northeastern Ohio, approximately 20 facilities per year. Since this is a two-year study, we anticipate that we may have other facilities that will join the study for the second year, as well as some changes in the facilities. If any new facilities join the study, we will notify the IRB of the changes.

We have received agreement currently from Seqirus (maker of adjuvanted vaccine), and are talking with Sanofi Pasteur (maker of high dose vaccine), to donate regular dose flu vaccine for use by employees at any participating LTC facility. This will be used as an incentive to the facility to agree to let us be a recruitment site. The vaccine will be sent directly from the manufacturer as a donation to the employee health team at the LTC site, so that we do not have to be involved in the handling, prescribing, or monitoring of the vaccine. If a LTC facility agrees to allow us to enroll, we will provide the manufacturer with the name and contact at the facility. We do not believe this is a coercive relationship with the long term care facility because they will get the vaccine once they agree to participate for the season, regardless of whether we recruit one or many from their site. We will also give all participating facilities an \$1000 participation stipend, to cover any administrative and staff costs that participation in the study may incur. The nursing and administrative staff (administrator, DON, ADON, Social Worker, Unit Nurses) at the long term care facility support the study in the following ways; they review the census with the study team during our initial meeting and prescreening, and help identify those residents that meet study inclusion criteria, and those residents that are not eligible for recruitment due to study exclusions. Additionally, the LTC administrative and nursing staff (Social Worker, Director of Nursing, Assistant Director of Nursing, Unit Nurses) helps the study team identify which residents can self-consent, and which ones utilize a LAR for their health care decisions. The LTC facility nurses and social workers, also helps the study team to identify residents (location), discusses medical conditions of the potentially eligible residents to determine if they are still eligible for recruitment or self-consenting, discusses medical conditions with the study team of consented residents to determine if they are still eligible at the time of vaccination, reviews the enrolled residents' medical conditions with the study staff at the end of study participation to determine if they had the influenza virus and/or other medical conditions that the study will be documenting for the study. The long term care facility also supports the study on the day of vaccination, by providing a nurse who helps identify consented residents. With regards to the administrative support, a designated nurse, the Director of Nursing, or the administrator at the LTC facility is in touch with the study staff throughout the duration of the study. The study coordinator sends regular updates, as to which residents

consented onto this study. This is important so that the LTC facility nurse doesn't consent a resident for their own flu vaccine, when the resident and/or LAR already consented onto the study. The LTC facility staff is not involved in any recruitment activities for the study, but lends support to the study team with regards to medical information and updates, and on vaccination and blood work days.

Consenting will take place at various long term care facilities in Northeastern Ohio and with an IRB approved written Consent Form, which we will review with either the resident or the LARs on the phone. We will speak to the LTC Administrator, Director of Nursing, Assistant Director of Nursing, Social Worker, and Unit Nurses to determine if a resident can make their own health care decisions and consent for their routine care, or if a Legally Authorized Representative (LAR) is needed. If the nursing staff deems that the resident can consent for themselves, we will approach them directly to initiate the consenting process. The consent process should take approximately 60 minutes, with ample time devoted to reviewing the Consent Form in detail, and our study staff asking the resident several questions about the study to confirm they have an understanding. If the resident is not able to understand the study, we will proceed to the LAR consent. If the nursing staff (LTC Administrator, Director of Nursing, Assistant Director of Nursing, Social Worker, and Unit Nurses) deems that the resident cannot physically or mentally give informed consent, as documented in their facility medical record, we will send an IRB approved Study Consent Form, Letter to LARs, LTC Facility Letter of Support, Study Brochure, and addressed stamped envelope to these potential subjects' LAR. We will follow up with a phone call to review the Study Consent Form and if they would like to enroll their family member onto the study, we will ask them to appropriately sign the Consent Form and send it back to us, in the provided envelope. If a resident is physically and mentally able to sign an Assent Form, the study staff will review the Assent Form with the resident. If a subject is determined to be physically or mentally not capable of signing any documents, (as documented in the medical records and confirmed by the Director of Nursing, Assistant Director of Nursing, Social Worker, and/or Unit Nurse), then we will waive Assent and will file the medical documentation along with the LAR consent. LARs will be mailed a copy of the signed Consent Form for their records, and we will provide a copy to the nursing administration at the LTC facility. The Consent Form will have study contact information, so they can withdraw consent at any time.

This process will begin months before the anticipated vaccination time frame, to allow plenty of time for mail correspondence, phone calls, and consenting.

The research team will make sure that the residents and LARs understand that participation is voluntary, and if they choose not to enroll onto the study, they will receive the standard of care flu vaccination that the LTC facility provides.

For year 2 of the study, we will be modifying the recruitment plan as follows:

The study team will meet with the LTC Administrator, Director of Nursing, Assistant Director of Nursing, Social Worker, and Unit Nurses to review the study, sign a Letter of Agreement to collaborate on the study, and narrow down the census to those residents who meet the study's inclusion/ exclusion criteria. From there, the study team and Director of Nursing, Assistant

Director of Nursing, Social Worker, and/or Unit Nurses will come up with a list of residents who are possibly eligible for recruitment onto the study. For those residents who need an LAR, a pre-recruitment letter from the LTC facilities administration will be sent out. This letter would give an overview of the study, state that the LAR will be receiving more details about the study in a future mailing from the study team, and also state that if the family member prefers NOT to receive any communication from the study team, please call the LTC facility to let them know. The study team will suggest to the LTC facility nursing team and administrator to also pre-communicate about the study through an email and /or newsletter that will let the residents and family members know about the study in advance of the study team's mailing.

